1.2. Secondary Objective

Determine if panitumumab-IRDye800 can identify sentinel nodes with the same accuracy as Lymphoseek.

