Sentinel node biopsy vs elective regional node dissection: Besides decreased morbidity, SNB offers other advantages over a neck dissection: i) Identification of aberrant draining patterns and “skip metastasis” (35–37); and ii) Improved (micro-) metastasis identification at (histo-)pathology; fewer SNs are harvested which are more meticulously evaluated by the pathologist, resulting in improved diagnostic accuracy (38,39). However, challenges remain: i) Local tracer injection is complicated in areas deep in the oral cavity; ii) Near-injection site SN identification can be challenging due to overshadowing of signal at the primary tumor signal (40,36,22); iii) Often multiple SNs are identified during surgery (22) increasing the risk of complications (41) (eg, nerve damage, lymphedema, scar tissue formation); iv) neck dissection after a positive SNB is complicated due to the presence of scar tissue; and v) A false-negative SNB occurs in 3 to 10% of subjects (ie, the SN is tumor-negative, but at follow-up metastasis in remaining regional LNs are found (42–45). Moreover, although LN mapping is superior to radiographic and clinical exam, it is still limited by the need for direct injection of the dye or radiolabeled compound. **Upstaging with LN assessment can thus only be assessed in tumor types that are accessible for local injection.** This is significant because it influences standard of care (LN surgery or complete lymphadenectomy) in these subject populations only. Identification of regional disease will inform prognostic information and/or determine the need and extent of adjuvant therapies for additional tumor types. Most importantly, however, the tracers used for SNB are not tumor-specific and thus SNB, similar to neck dissection, does not allow for intraoperative tumor-positive LN identification (21,46,47). In fact, **for both SNB and neck dissection (histo-)pathological evaluation is required to determine the presence of (micro-) metastasis and thus a method to intraoperatively identify metastatic LNs is lacking.** Thus, HNSCC subjects would benefit from an alternative technique that, allows for intraoperative lymph node staging.

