2.4.3.2. Preoperative Sentinel Node Mapping

Currently, SNB of squamous cell carcinoma of the head and neck is not performed at Stanford. It is however in the NCCN guidelines (7) where it is advocated as an alternative to neck dissection for loco-regional staging of the neck in subjects with either T1 or T2 stage and N0 status. For the subject work-up we will follow literature references on Lymphoseek in HNSCC (28), and the standard operating protocol the Division of Nuclear Medicine has in place for SNB of melanoma using Lymphoseek.

Current Procedural Terminology (CPT) codes are available for injection of the radiopharmaceutical Lymphoseek and (sentinel) lymph node mapping (38792 and 78195, respectively) in oral cavity cancer (ICD-10 codes C01-C06.9). The costs of the SNB procedure will therefore be billed to the subject's medical insurance.

Lymphoseek will be locally administrated the day before surgery. Peritumorally, 4 x 0.1 mL of Lymphoseek will be administrated. A total dose of maximally 2 mCi will be administered (28). Further details on Lymphoseek administration and radiation exposure are described in 4.1 and 4.3, respectively.

Preoperative SN mapping in subjects with HNSCC will be performed according to the protocol the Division of Nuclear Medicine has for Lymphoseek-based SN mapping in melanoma. Dynamic images will be acquired in anterior projection over the head and neck starting immediately after the injections have been completed. Lymphoscintigraphic imaging is performed at a 1 minute/frame for 30 minutes using a 128x128 matrix, followed by static spot views with/without a transmission source. Single photon emission computed tomography combined with computed tomography (SPECT/CT) imaging of the head and neck will follow the planar dynamic imaging. Acquisition parameters for a multi-detector system are 3-degree angular sampling, 128 x 128 matrix, 360-degree rotation and 20-30 sec per stop.

Following completion of image acquisition the Nuclear Medicine physician will review the images to determine the direction of the lymphatic flow and the potential accumulation in a sentinel LN. Using SPECT/CT images, he/she will determine the number and location of the SNs.

Rationale for SPECT/CT imaging: The value of SPECT/CT lies in the anatomical localization of the spot views seen on the dynamic planar images. Moreover, SPECT/CT may help to localize foci of abnormal Lymphoseek accumulation more accurately than planar imaging or SPECT alone.

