2.4.3.3. Intraoperative Imaging Protocol

On the day of surgery, 1 to 5 days post-infusion of panitumumab-IRDye800, intraoperative fluorescence imaging and gamma tracing will be performed.

Optical imaging devices to be used: Imaging with the optical imaging devices will be performed intraoperatively *in situ* and on the back table (see Appendix B for a list of the imaging devices). Additional ex vivo devices will also be used to image the specimens on the back table (see Appendix B for a list of the imaging devices).

All in vivo devices are FDA approved for measuring intraoperative blood flow after indocyanine green (ICG) injection. Because IRDye800 and ICG have overlapping excitation and emission spectra, each device can also be used for imaging subclinical disease based on our preclinical studies in head and neck cancer (see Appendix B for a list of the imaging devices).

Sentinel node biopsy (stage T1/2, cN0)

Step 1) *In situ* gamma tracing and fluorescence imaging of the sentinel nodes:

1. Prior to opening the skin, the surgeon will screen the neck for the presence of radioactive node(s) (ie, SNs) by sweeping the gamma probe over the intact neck. If any radioactive nodes are detected, the location of detected radioactive nodes will be marked on the skin using indelible ink and a still image of the marked will be collected for documentation.
2. After opening the skin, a photo of the neck will be taken for documentation. Hereafter the surgeon will perform fluorescence imaging of the neck to evaluate if there are any fluorescent nodes visible. Fluorescent nodes will be marked on the photo of the neck. Video and still images of the fluorescence imaging procedure will be collected.

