3. Hereafter, as per standard of care, the surgeon will perform SNB using the gamma probe. For this, the surgeon will evaluate the neck with the gamma probe for the presence of radioactive nodes. Upon localizing of radioactive nodes, the count rate of the node will be determined. Then, just prior to the resection of the radioactive node, *in situ* fluorescence imaging will be performed to evaluate the fluorescence-based visibility of the node. For each radioactive node, the respective *in situ* location will be documented (level Ia, Ib, IIa, IIb, III, IV or V) as well as the radioactive status (count rate) and fluorescence status (yes/no). Hereafter the node will be harvested by the surgeon. This process will be repeated until no radioactive nodes are detected anymore *in situ*.

Step 2) Wound bed imaging:

As per standard of care SNB, upon completion of SNB, the neck will be screened once more with the gamma probe as such to determine the presence of any remaining radioactivity (ie, a radioactive signal detected > 10% of the background that correlates with any substrate (node). Areas in the wound bed determined radioactive-positive will be surgically re-evaluated, and, upon checking the fluorescence-status, removed, if deemed necessary by the surgeon. If any nodes are found, gamma tracing will be performed to determine the radioactive status.

Step 3) Pathological imaging:

The fluorescence and/or radioactive status of all excised nodes will be confirmed *ex vivo* on the back table using both a closed-field imaging device and an open-field device as well as the gamma probe, respectively. Hereafter all excised nodal specimens will be sent for (histo-)pathology. After the tissue has been processed and evaluated by the pathologist, imaging findings will be compared to gold-standard histological-assessment performed by the pathologist (including a hematoxylin and eosin (H&E) staining) to determine the correlation between fluorescence, radioactivity and the presence/absence of tumor tissue in the LN(s). Also findings will be compared to preoperative lymphoscintigraphy and SPECT/CT imaging (ie, correlation between preoperative imaging findings and intraoperative imaging findings).

Neck dissection only (T1-4, cN+)

After the neck has been opened by the surgeon, it will be inspected by the surgeon for the presence of suspicious nodes. Real-time fluorescence imaging of the LNs in the neck will then be performed at 4 time points:

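### In Cohort 1 the open-neck gamma search and the verification of residual radioactive areas are not shielded from the dye result, and Section 12.1.2 does not say which Lymphoseek reading is analysed

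*Combined protocol and SAP*

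**What the plan says.** The secondary objective (Section 1.2) reads: "Determine if panitumumab-IRDye800 can identify sentinel nodes with the same accuracy as Lymphoseek". Section 12.1.2 turns this into sensitivity and specificity for Lymphoseek, plus the odds of a false negative with the dye relative to Lymphoseek-based SNB.

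Sections 2.4.3.2 and 2.4.3.3 set this order for Cohort 1:

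1. The day before surgery, the nuclear medicine physician reads the scans: "Using SPECT/CT images, he/she will determine the number and location of the SNs".
2. Before incision there is a gamma sweep of the intact neck: "Prior to opening the skin, the surgeon will screen the neck for the presence of radioactive node(s) (ie, SNs) by sweeping the gamma probe". Hot spots are inked on the skin and photographed.
3. The skin is opened and the neck photographed. "Hereafter the surgeon will perform fluorescence imaging of the neck to evaluate if there are any fluorescent nodes visible". Any such nodes are marked on the photograph.
4. "Hereafter, as per standard of care, the surgeon will perform SNB using the gamma probe". Within this step, "Upon localizing of radioactive nodes, the count rate of the node will be determined"; that node's fluorescence is imaged next, and it is then harvested. The cycle repeats until the probe finds nothing more.
5. The wound bed is screened again with the probe (Step 2): "Areas in the wound bed determined radioactive-positive will be surgically re-evaluated, and, upon checking the fluorescence-status, removed, if deemed necessary by the surgeon".
6. Both signals are checked ex vivo on every excised node, and the nodes go to histology (Step 3).

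Section 2.4 states that the study is unmasked. Section 4.5 states that what the imaging shows plays no part in diagnosis or medical decisions.

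**The concern.** A comparison of two tracers is cleanest when each is read without knowledge of the other. Here the surgeon who runs the open-neck probe search has already seen and marked the fluorescent nodes. No second operator and no locked gamma reading is described at that stage. A node that the probe alone might pass over could attract a closer search because it was seen to fluoresce, and then be counted as a Lymphoseek detection. Section 2.1 gives a setting where the probe is weak: "Near-injection site SN identification can be challenging due to overshadowing of signal at the primary tumor signal".

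Step 2 raises a second issue. The fluorescence check sits between finding residual radioactivity and deciding on removal. Cohort 1 has SNB only, and histology covers excised tissue only. A radioactive, non-fluorescent area left in place is therefore never verified, and it is exactly the kind of area that could be a dye false negative.

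At stake is the interpretation of the false-negative comparison, which Section 12.1.2 singles out as the particular worry.

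**Working it through.** **Which Lymphoseek readings precede the dye?**

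| Reading | Fluorescence already seen? |
|---|---|
| SPECT/CT number and location (2.4.3.2) | No |
| Pre-incision gamma sweep (2.4.3.3, Step 1 item 1) | No |
| Open-neck probe search (Step 1 item 3) | Yes, the neck survey; each count rate still precedes that node's own pre-resection image |
| Residual areas in the wound bed (Step 2) | Area found by probe first; removal decided after the fluorescence check |

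Two readings are free of the dye and two are not. Section 12.1.2 names none of them as the one analysed.

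**Does Section 4.5 close the gap?** It bars use of imaging in decisions, but Step 2 places a fluorescence check immediately before a removal decision. Section 4.1 has nodes evaluated and scored by fluorescence and radio-tracing together, and Section 4.8 says the study agents may help the surgeon see where nodes are. These passages need reconciling; Section 4.5 alone does not shield the reading.

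**How much could one node matter?** The plan gives no figure for this point. The effective sample size in Section 12.1.3 reproduces, 600 / (1 + 29 × 0.005) = 524.0, but it models correlation of nodes within a person, not dependence between the two readings.

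- Cohort 1: 10 subjects (Table 1). Occult disease in cN0 patients: 10 to 30% (Section 2.1). So 10 × 0.10 = 1 to 10 × 0.30 = 3 node-positive subjects.
- Assumption, not in the documents: 1 to 2 positive nodes per such subject, giving 1 to 6 positive nodes.
- One node is then 1/6 = 17 points to 1/1 = 100 points of sensitivity.

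This is only 1/n. It would fit any single-node error and does not estimate how often the dye influences the reading.

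**Which way would it push?** Take an illustrative set of 6 positive nodes, all verified: 4 positive on both tracers, 1 on the dye only, 1 on Lymphoseek only. Both sensitivities are 5/6 = 83%.

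- Survey prompts a probe detection: the dye-only node becomes positive on both. Lymphoseek 6/6 = 100%, dye 5/6 = 83%.
- Radioactive, non-fluorescent node left in place: it leaves the table. Dye 5/5 = 100%, Lymphoseek 4/5 = 80%.
- Both occur: 5/5 for each.

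The first route favours Lymphoseek and the second favours the dye. Each removes one discordant node. The illustration sets aside a separate matter: Step 1 describes harvest of radioactive nodes only, so a dye-only node may not reach histology at all.

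**The case against.** The strongest reply is that radioactivity drives everything in Cohort 1. The probe locates the node, its count is taken before its own fluorescence image, and harvest continues until no radioactive node remains. Dye-negative radioactive nodes found in Step 1 are therefore removed and verified. In Step 2 the area is classed as radioactive before the dye is checked, and the check may be there only for the record. The endpoint is a node's Lymphoseek status, confirmed ex vivo, so a node with counts did take up the tracer. The dye also lights up the primary tumour, so it need not be clearer than the probe near the injection site.

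Most of this stands. It confines the unverified-tissue problem to Step 2 and makes the survey effect a possibility rather than an observed fault. It does not remove the point. Uptake in a node is not the same as the probe finding it unaided, and the wording of Step 2 does not limit the fluorescence check to documentation.

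A reader might infer that the whole comparator is dye-informed SNB, or that the design drives the result toward equal accuracy whatever the truth. The documents support neither. SPECT/CT and the pre-incision sweep are free of the dye. In the illustration, either route alone creates a difference between tracers that are truly equal.

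A reader might also want the pre-incision list to become the main Lymphoseek call. That would replace SNB, which includes the open-neck search, with a weaker test.

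**Conclusion.** The point holds in a limited form. The open-neck gamma search and the verification of residual radioactive areas are not protected from the dye result, and Section 12.1.2 leaves the analysed Lymphoseek reading unstated. Whether the dye changes any call is a risk, not a finding; its frequency and its net direction between tracers cannot be computed from the documents. Its importance comes from the small number of positive nodes expected: 1 to 6 in Cohort 1, if node-positive subjects have 1 to 2 positive nodes each. This calls for a clarification and a sensitivity analysis in a trial that Section 2.4.1 describes as exploratory; it does not invalidate the comparison.

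**What to change.** 1. State in Section 12.1.2 that the main Lymphoseek call is the as-operated gamma-guided SNB.
2. Flag each node first marked on the fluorescence survey that appears on neither the SPECT/CT list nor the pre-incision skin marks. Pre-specify a sensitivity analysis that does not credit these nodes to Lymphoseek, and show both results.
3. In Step 2, record the gamma-based judgement on each residual area before fluorescence is viewed.
4. Report radioactive areas left in place as unverified. With TP dye-positive nodes among n verified tumour-positive nodes, and u radioactive, non-fluorescent areas left in place, give the worst-case dye sensitivity TP / (n + u). For example, 5/6 = 83% becomes 5/7 = 71% with one such area. The same assumption makes each of these areas a true positive for Lymphoseek.
5. Reconcile Step 2 with Section 4.5. Removal decisions stay with the surgeon.

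The cost is a form field, matching of nodes by neck level to SPECT/CT and skin marks, and a second analysis. The survey photographs and the planned comparison with preoperative imaging (Step 3) already supply most of the data. The downside is that the sensitivity analysis may understate Lymphoseek, because the pre-incision list can miss nodes that the probe alone would find after incision. That is why it should sit beside the main analysis and not replace it.

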2.4.3.4. Laboratory Imaging Protocol

Once the LNs have been removed from the subject and sent for pathology review, additional imaging will be performed with non-significant risk devices (Pearl and Odyssey imaging systems – LICOR Biosciences, Lincoln, NE) of pathological specimen(s) using non-invasive imaging modalities that do not expose the subject to radiation or other interventions, or alter the standard pathological processing of the tissues (see Appendix B for a list of the imaging devices). Normal waste tissues will also be imaged. The research imaging modalities will not be used in the patient-care setting. Imaging will be done in collaboration with the Department of Pathology to ensure preservation of tumor-related information. Data from the research use of the device will not be used for diagnosis or other medical decision-making.

2.4.3.5. Pathological Correlates

Tissue specimens will be collected by pathology after which they will be formalin-fixed and paraffin-embedded according to standard procedures.

Specifically, for the LN specimens we will investigate the following:

To determine biological characteristics associated with fluorescence intensity measurements, formalin-fixed paraffin-embedded blocks from the collected specimens will be obtained from pathology after routine analysis and imaged on the Pearl and Odyssey as previously described in preclinical models (72,73). This will allow high-resolution evaluation of the location of the fluorescence signal in the tissue. Subsequently 5 micron sections will be cut for histological analysis of: 1) Size of the epithelial tumor compartment in percent of total; 2) Tumor characteristics (ie, size, proliferation); and 3) EGFR. Methods have been previously described by us using *in vivo* models (74–78).

We will then determine if these characteristics are associated with fluorescence (yes/no) from the Pearl and Odyssey imaging systems. We will use the two-sided Fisher's exact test to determine the level of association between tumor characteristics (ie, size, proliferation) and EGFR status and fluorescence (yes/no). Likewise, we will test the association between the size of the epithelial tumor compartment and fluorescence (yes/no) with the two-sided Wilcoxon rank sum test.

To determine where panitumumab-IRDye800 localizes in the fluorescent LNs, 5 micron sections will be cut and undergo immunohistochemistry for localization of various immune cells, including B and T-cells, macrophages and dendritic cells. Immunohistochemistry findings will then be correlated with fluorescence intensities measured on the Pearl and Odyssey imaging systems. We expect that panitumumab-IRDye800 both specifically and non-specifically occurs in the LNs. Specific uptake in the LNs will occur if metastasis are present in the nodes. Non-specific uptake of panitumumab-IRDye800 in the LNs can occur by a mechanism similar to the principle of SNs mapping, ie, due to accumulation of tracer at the injection site, overflow from the tumor to the LNs will occur where this tracer will get trapped in immune cells (79).

The two-sided Fisher's exact test will be used to determine the level of association between each of these characteristics and panitumumab-IRDye800 fluorescence (yes/no).

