12. STATISTICAL CONSIDERATIONS

12.1 Statistical Design

12.1.1. Primary Objective and Endpoint

The **primary objective** of the study is to determine if near-infrared fluorescence imaging of panitumumab-IRDye800 can identify metastatic disease in regional neck LNs of subjects with HNSCC.

The **primary endpoint** is: The number and location of panitumumab-IRDye800 positive LNs that are also tumor-positive at (histo-)pathology.

To **answer the primary objective**, we will calculate the sensitivity and specificity of the intraoperative findings on whether the LN is fluorescent (ie, presence of panitumumab-IRDye800) to the histopathological (gold standard) status of the LNs.

We will use the matched pair Durkalski's test (80), accounting for the cluster-correlation within subject, for all sensitivity and specificity comparisons (primary and secondary) using the clust.bin.pair package (81) in the R statistical software (84). Significance for both primary and secondary analyses will be assessed at the 0.05 level and to assess uncertainty, 95% confidence intervals will be provided for all estimates.

Descriptive statistics for continuous characteristics (eg, size of the tumor compartment) will include mean, standard deviation, median, interquartile range, minimum, and maximum values. Frequencies and percentages will be used to summarize categorical data. Graphical tools such as heat maps, histograms, and boxplots will be used to assess distributional properties of continuous variables.

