12.1.3. Sample Size Justification and Power Considerations

We expect to enroll 10 T1/T2 node-negative subjects and 10 subjects with T1-4 and LN metastasis. Based on the data on LN collection from our current IRB-35064 study, we expect that 50% of subjects will undergo a bilateral neck dissection, meaning we would have a total of 30 necks. Assuming an average of 20 LN harvested per neck we would have a total of 600 LNs. Based on previous findings from our IRB-35064 study, we expect approximately 30-40% of subjects (6 to 8 of 20) will have metastatic LNs with an overall prevalence of 5 to 10% of the total number of harvested LNs (30 to 60 of 600) being tumor-positive.

Since this is a Phase 2 study, power considerations are limited but even so, we have excellent power to detect differences in specificity. Although we will use Durkalski's test to compare sensitivities and specificities, we estimated power by first determining the effective sample size (ESS), adjusting for the correlation of LNs within person, and then estimated power using McNemar's test on this ESS. We assumed an intra-class correlation of 0.005, yielding an effective sample size of 524 LNs. With an effective sample size of 524, a prevalence of 7.5%, a significance level of 0.05, and a 0.25 proportion of discordant pairs, we have greater than 99% power to detect a 0.1 difference in specificities, assuming the lower specificity is 0.8. Similarly, we have greater than 78% power to detect a 0.2 difference in sensitivity with the one-sided McNemar test. This assumes the proportion of discordant pairs is 0.25 and the lower sensitivity is 0.75.

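### The lymph-node correlates in section 2.4.3.5 use Fisher and Wilcoxon tests that ignore nodes sharing a subject, so their p-values can be too small, by an amount the documents do not fix

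*Combined protocol and SAP*

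**What the plan says.** Section 2.4.3.5 concerns lymph-node specimens, so the node is the natural unit. It lists three sets of tests against fluorescence read on laboratory imagers:

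- Tumour size, proliferation and EGFR status: "We will use the two-sided Fisher's exact test to determine the level of association between tumor characteristics".
- Epithelial compartment size: "we will test the association between the size of the epithelial tumor compartment and fluorescence (yes/no) with the two-sided Wilcoxon rank sum test".
- Immune-cell findings: "The two-sided Fisher's exact test will be used to determine the level of association between each of these characteristics and panitumumab-IRDye800 fluorescence (yes/no").

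The section does not mention that several nodes come from one subject. Section 2.4.3.6 sends the reader to section 12 for the statistics. Section 12.1.1 names Durkalski's test, "accounting for the cluster-correlation within subject, for all sensitivity and specificity comparisons (primary and secondary"). Section 12.1.3 computes an effective sample size, "adjusting for the correlation of LNs within person", and gives the only ICC in the documents: "We assumed an intra-class correlation of 0.005". Nothing extends either step to the correlates. On the significance level, section 12.1.1 says "Significance for both primary and secondary analyses will be assessed at the 0.05 level"; none is set for the correlates.

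**The concern.** Fisher's exact and the Wilcoxon rank sum test treat every node as a separate piece of evidence. The plan itself says nodes within a person are correlated, then uses tests that assume they are not.

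The p-value is affected only if both variables cluster. The documents give reasons why they might, but no sizes. For fluorescence, all nodes of a subject share one infusion and one interval of 1 to 5 days to surgery (section 9.1, footnote 8). For a characteristic, section 2.1 describes EGFR overexpression by subject. Section 12.1.3 expects all 30 to 60 tumour-positive nodes to come from only 6 to 8 subjects, so a few people could drive what is reported as a node-level association.

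At stake is the reading of specific versus non-specific uptake, which these tests are meant to inform.

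**Working it through.** **1. The plan's own figure.** With 600 nodes in 20 subjects, m = 600/20 = 30. Effective sample size = 600/(1 + 29 × 0.005) = 600/1.145 = 524, as stated. With 20 nodes per neck as the cluster it would be 548, so the plan treats the subject as the cluster.

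**2. Formula for an association.** When two independent variables cluster in the same subjects, the variance of their association grows by about DE = 1 + (m − 1) × ICC₁ × ICC₂. A nominal two-sided 5% test then has size of about 2 × [1 − Φ(1.96/√DE)].

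**3. At the plan's ICC for both variables.** DE = 1 + 29 × 0.005² = 1.001, so there is no inflation.

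**4. Tumour-positive nodes.** Section 12.1.3 gives 30–60 nodes in 6–8 subjects, taken here as 8×4, 7×6 and 6×10 (subjects × nodes). The assumptions are a fluorescence ICC of 0.3 and 75% of nodes fluorescent (the lower sensitivity in section 12.1.3).

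| Layout | DE, both ICCs 0.3 | Size by formula | DE, characteristic constant within subject | Size by formula |
|---|---|---|---|---|
| 8×4 | 1 + 3 × 0.09 = 1.27 | 8% | 1 + 3 × 0.3 = 1.9 | 16% |
| 7×6 | 1 + 5 × 0.09 = 1.45 | 10% | 1 + 5 × 0.3 = 2.5 | 21% |
| 6×10 | 1 + 9 × 0.09 = 1.81 | 15% | 1 + 9 × 0.3 = 3.7 | 31% |

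Simulation used beta-binomial fluorescence with an independent characteristic, binary for Fisher and normal for Wilcoxon. It gives about 4–11% (Fisher) and 7–14% (Wilcoxon) with both ICCs 0.3. With a constant characteristic it gives about 6–28% and 14–31%. Fisher is lower because it is conservative in small tables. With both ICCs at 0.1, no case exceeds about 6%.

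**5. The same nodes at 97.2% fluorescent** (the earlier antibody's sensitivity, section 2.1). Only about 1 to 2 nodes are non-fluorescent. With both ICCs 0.3, simulated size is 0.6–2.6% (Fisher) and 2.1–5.4% (Wilcoxon), so the tests are mostly conservative.

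**6. All nodes.** One route to a fluorescence ICC is that some subjects have metastases and others do not: ICC = (Se + Sp − 1)² f(1 − f)q² / [P(1 − P)]. Here f is the share of subjects with metastases, q = prevalence/f, and P is the share of nodes fluorescent.

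- Accuracy 97.2%/92.7% (section 2.1), prevalence 10%, 6 of 20 subjects: P = 0.972 × 0.10 + 0.073 × 0.90 = 0.163, and ICC = 0.899² × 0.21 × 0.111/(0.163 × 0.837) = 0.14.
- Same accuracy, prevalence 5%, 8 of 20 subjects: ICC = 0.03.
- Accuracy 75%/80% (the lower values in section 12.1.3): ICC = 0.006 to 0.037.

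The characteristic is assumed to have the same ICC. Layouts were 20×30, or 3 nodes per sentinel-node subject (assumed) with 20 or 40 per dissection subject. Simulated size is about 5–6% at ICC 0.03 and 8–13% at ICC 0.14. For 20×30 at ICC 0.14 the formula gives DE = 1 + 29 × 0.0196 = 1.57 and a size of about 12%.

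**The case against.** The strongest reply is that inputs taken from the documents show little harm. The only stated ICC gives no inflation, and the planning accuracies of 75% and 80% lead to ICCs that leave the all-node tests near 5%. A very high fluorescence rate makes the tumour-positive tests mostly conservative. The value of 0.3 has no source in the plan. Clustering of the characteristics is thinly supported: the EGFR figure in section 2.1 is a prevalence among subjects, not a within-subject correlation, and nothing is given for size, proliferation or immune cells. The study calls itself exploratory (section 2.4.1), and no decision depends on these p-values.

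Most of this stands, and it limits the point to a possible error of unknown size. It does not remove it. The 0.005 was assumed for the sensitivity/specificity power calculation, not for laboratory fluorescence, EGFR or immune-cell measures. Conservatism at high fluorescence rates is no safeguard at lower ones. If EGFR status is largely a property of the subject, the constant-within-subject case is the relevant one.

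A reader might infer stronger things that the documents do not support:

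- That the p-values will be too small. The direction depends on ICCs and fluorescence rates that are not given.
- That all-node error reaches 13–17%. This needs 57 nodes per dissection subject, (600 − 10 × 3)/10, whereas section 12.1.3 assumes 20 per neck, hence about 40 for a bilateral dissection.
- That the main results are compromised. Section 12.1.1 specifies a clustered test for the sensitivity and specificity comparisons.

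**Conclusion.** The concern holds as a minor one. Section 2.4.3.5 names tests whose independence assumption conflicts with section 12, and no other section repairs this. The consequence ranges from none, or conservative tests, to a type I error several times nominal when a characteristic barely varies within subject and fluorescence clusters substantially.

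The figures rest on assumed ICCs, equal nodes per subject except in the split layouts, and intraoperative or earlier-antibody accuracies carried over to laboratory readings of tissue blocks. They are a range of what could happen, not an estimate of what will. Only exploratory correlates with no stated significance level are affected.

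**What to change.** In section 2.4.3.5, replace the ordinary tests with analyses that treat the subject as the cluster:

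- For characteristics that vary within subject, use a subject-stratified permutation test or a clustered rank sum test. Where all 20 subjects contribute, GEE with a small-sample correction is an alternative.
- For a characteristic constant within subject, use a between-subject comparison, since a stratified permutation cannot test it.
- Where non-fluorescent nodes are too few, report Fisher and Wilcoxon descriptively and base no association claim on their p-values.

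In simulation the alternatives hold their level. For tumour-positive nodes at 75% fluorescent and ICCs of 0.1–0.5, the clustered rank sum test has size 2.0–4.1%. The stratified permutation test has 2.5–5.6% for a continuous characteristic and 0.1–2.9% for a binary one.

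The cost is a few sentences, a little code and some power. For an assumed true association (log-odds 1.0 per SD, latent ICC 0.3, 75% fluorescent; 8×4, 7×6, 6×10), ordinary Wilcoxon rejects in 41/51/65%, the stratified permutation test in 28/38/55% and the clustered rank sum test in 22/21/23%. The ordinary test's figures are not adjusted for its inflated size. At 97.2% fluorescent every method is weak, which is why descriptive reporting is reasonable there.

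As a separate clarification, state which nodes enter each test. The immune-cell work is introduced with "To determine where panitumumab-IRDye800 localizes in the fluorescent LNs" but is then tested against fluorescence yes/no, which needs non-fluorescent nodes as well.
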